3.16.4. Procedures After Study Drug Treatment

Patients who participate in the study in compliance with the protocol for at least 24 weeks of double-blind treatment will be considered to have completed the treatment period. Patients who complete the follow-up visit (approximately week 32) will be considered as having completed the study. See Section 12.4 for the definition of the end of the study.

Patients who discontinue the study drug prematurely must be encouraged to continue to attend the regular scheduled visits and complete the prescribed safety and efficacy evaluations through the EOT/early withdrawal visit and the follow-up visit, if at all possible (see Section 4.5).

Patients who both discontinue the study drug and also withdraw from the study should have final evaluations performed on the last day they receive the study drug or as soon as possible thereafter. Patients should also return for the follow-up visit and procedures if at all possible (see Section 4.5).

Procedures for patients who withdraw prematurely from the study are described in Section 4.5. Following termination of the study, patients should be treated according to the standard of care, and as guided by the principal investigator.

Patients with ongoing adverse events or clinically significant abnormal laboratory test results (as interpreted by the investigator) will be monitored as described in Section 7.1.2 and Section 7.3, respectively.

The following procedures/assessments will be performed at the follow-up visit (EOT + 8 weeks \pm 7 days [visit 20]):

- Hematology tests (CBC with differential)

- Collect blood for serum reslizumab concentration determination (PK assessment)
- Collect blood sample for immunogenicity assessment
- Concomitant medication inquiry
- Adverse event inquiry
- Perform urine pregnancy test

The following procedures/assessments will be performed at the late follow-up visit (EOT + 24 weeks \pm 14 days [visit 21]):

- Collect blood for serum reslizumab concentration determination (PK assessment)
- Collect blood sample for immunogenicity assessment

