4.5.1. Discontinuation of Study Treatment

If premature discontinuation of study treatment occurs for any reason, the patient should continue attending remaining study visits while off study treatment. The patient will continue to receive study provided OCS (prednisone) treatment for the remainder of their participation in the study. The patient should not be considered withdrawn from the study due to interruption or discontinuation of study treatment. For this study, it is very important to continue collecting data from all patients whether or not they complete treatment.

If premature discontinuation of study treatment occurs, the patient should return to the clinic as soon as possible for a study treatment discontinuation visit. All evaluations should be performed as specified in the protocol for the early withdrawal visit (see Table 5). The investigator must determine the reason for and the date of discontinuation of study treatment and record this information in both the source documentation and the Study Drug Treatment Completion CRF. The patient's continued participation in the study must be discussed by the investigator and site staff with the patient; the investigator and site staff must also request the patient to continue attending study visits according to the study visit schedule with all assessments completed up to week 24 (visit 19). The OCS dose and safety assessments at week 24 (visit 19) are the priority assessments for patients that prematurely discontinue study treatment. At a minimum, the investigator should make every effort to obtain information regarding serious adverse events, OCS dose, and survival status at week 24. A safety follow-up visit (visit 20) should be conducted 8 weeks after visit 19.

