4.5.2. Complete Withdrawal from Study

If a patient decides to completely withdraw from the study (ie, refuses any further study participation or contact), all study participation for that patient will cease and all data to be collected at subsequent visits will be considered missing. If a patient decides to completely withdraw from the study, every effort should be made to complete and report the observations outlined in Section 4.5.1 (Discontinuation of Study Treatment) before withdrawal. A complete final evaluation at the time of the patient's withdrawal should be made, including an explanation of why the patient is withdrawing from the study. The reason for and date of withdrawal from the study must be recorded in the source documentation and the Double-Blind Treatment Period Completion CRF.

For patients who are lost to follow-up (ie, patients whose status is unclear because they fail to appear for study visits without stating an intention to withdraw), the investigator should make appropriate efforts to re-establish contact with patient; attempts to contact the patient should be documented in the source documents. If contact has not been re-established, efforts should still be made to locate the patient and obtain information regarding serious adverse events, OCS dose, and survival status at the end of the 24-week treatment period. A patient should only be designated as lost to follow-up if the site is unable to establish contact with the patient after 3 documented attempts via 2 different methods (phone, text, e-mail, certified letter, etc).

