5. TREATMENT OF PATIENTS

5.1. Drugs Administered During the Study

After successfully meeting entry criteria, eligible patients will be randomly assigned to study drug (110 mg of reslizumab or placebo) with stratification based on maintenance OCS dose of >10 mg or ≤10 mg and age (12 to <18 years of age or 18 years of age or older) at baseline, using IRT, which uses computerized central randomization. Study drug will be administered by qualified study personnel as sc injections in the upper arm(s) once every 4 weeks for a total of 6 doses.

The pre-filled syringe has a staked 27G 0.5-inch needle. Subcutaneous injections can be given at a 90° angle or at a 45° angle. The injection can be given at a 90° angle if 2 inches of skin can be grasped between the thumb and first finger. If only 1 inch of skin can be grasped, the injection should be done at a 45° angle. The sites where injections are given should be at least 1 inch away from each other. Product should be removed from the refrigerator and allowed to equilibrate at room temperature for 15 to 30 minutes before administration.

Study drug will be administered by qualified study personnel who will ensure that the study drug is administered in accordance with the protocol. The needle shields of the prefilled syringes contain natural rubber latex, which may cause allergic reactions; see exclusion criterion (p). Additional information regarding study drug can be found in the Pharmacy Manual.

A more detailed description of the reslizumab drug product is provided in Section 3.11.1. Study drug exposure will be measured and compliance to study drug administration will be monitored.

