6.4.2.2. Analysis

The Kaplan-Meier (KM) method will be used to estimate and compare the distributions of time to first CAE between treatment groups. Time to first event will be analysed for on-treatment events.

The time period for the on-treatment analysis will extend from the date of first dose of study drug to the cessation of study treatment, defined as the date of the end of treatment (week 24) visit for patients who completed treatment and the date of last dose (+4 weeks) for patients who discontinued treatment early. Patients without an event during this time frame will be censored at either the date of the end of treatment (week 24) visit for patients who completed treatment or at the date of last dose (+4 weeks) for patients who discontinued early.

The hazard ratio (95% CI) and p-value will be estimated using a Cox proportional hazards regression model adjusting for the stratification factors.

The following sample SAS[®] code pertains to the analysis of time to first CAE.

```
proc lifetest data=<<>> outsurv=<<>>;
  time tcae*censor(0);
  strata treatment;
  ods output quartiles=<<>>;
run;
```

```
proc phreg data=<<>>;
  class treatment (ref='PBO');
  model ttcae*censor(0) = treatment / rl ties=discrete;
  strata strata1 strata 2;
  ods output parameterestimates=<<>>;
  ods output globaltests=<<>>;
run;
```

A KM plot will be provided for the time to first CAE by treatment group.

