APPENDIX A. IMPUTATION AND ANALYSIS STEPS FOR SENSITIVITY ANALYSIS OF THE PRIMARY VARIABLE

The following represents an outline of the planned methodology for the multiple imputation procedure for the sensitivity analysis of the primary OCS response variable. Minor deviations from this outline can be addressed in the discussion of the results in the CSR. In the situation that more significant updates are warranted, changes will be addressed in a SAP amendment to be finalized prior to database lock.

Step 1: Seed generation.

The seed generation utilized the code below, resulting in a seed (49476) that will be used in the analysis after unblinding.

```
data seed;
  seed = int(time());
  put seed=;
  call symput('seed', left(seed));
run;
```

Step 2: Classify patients with missing data.

Patients in this study will be partitioned into the following 3 categories:

1. ET0; patients who completed all 24 weeks of treatment
2. ET1; patients who withdrew early from treatment but remained in the study contributing post-treatment follow-up data through week 24
3. ET2; patients who withdrew early from treatment but elected not to remain in the study through week 24

Step 3: Imputation of missing data.

Missing values for OCS dose (continuous) at week 24 and at visits in which earlier OCS doses were missing will be imputed. The missing OCS dose will be imputed based on measurements observed at previous visits and treatment group, assuming data are missing at random (MAR). The resulting observations at week 24 will be categorized as per the primary endpoint.

If the pattern of missing data is monotonic, the MONOTONE method in PROC MI will be used for imputation with a linear regression technique.

```
proc mi data=&indata out=&outdata nimpute=10 seed=&seed;
  class treatment;
  monotone regression (week4=treatment base /details);
  monotone regression (week8=treatment base week4 /details);
  monotone regression (week12=treatment base week4 week8 /details);
  monotone regression (week16=treatment base week4 week8 week12 /details);
  monotone regression (week20=treatment base week4 week8 week12 week16 /details);
  monotone regression (week24=treatment base week4 week8 week12 week16 week20 /details);
  var treatment base week4 week8 week12 week16 week20 week24;
run;
```

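### Time to first CAE: event-free patients who leave the study early are censored at last dose + 4 weeks even if contact ended sooner, so up to 4 unobserved weeks each count as exacerbation-free

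*SAP*

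**What the plan says.** For time to first CAE, SAP 6.4.2.2 runs the on-treatment window from the first dose to the week 24 visit for completers, or to last dose + 4 weeks for early discontinuers. "Patients without an event during this time frame will be censored at either" the week 24 visit date, for completers, "or at the date of last dose (+4 weeks) for patients who discontinued early". Nothing in the section refers to the date of last contact or last CAE assessment.

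The protocol treats two kinds of early stopper differently:

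- **Stops drug, stays in the study.** Under Protocol 4.5.1 "the patient should continue attending remaining study visits while off study treatment". The minimum data to be sought are "information regarding serious adverse events, OCS dose, and survival status at week 24"; CAEs are not on that list.
- **Stops drug and leaves the study.** Under Protocol 3.16.4 such patients "should have final evaluations performed on the last day they receive the study drug or as soon as possible thereafter". After complete withdrawal (Protocol 4.5.2), "all study participation for that patient will cease and all data to be collected at subsequent visits will be considered missing".

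The SAP expects some of the second kind. Appendix A defines a category for "patients who withdrew early from treatment but elected not to remain in the study through week 24".

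**The concern.** Censoring is meant to mark the end of observation. If a patient leaves the study shortly after a dose without a CAE, the rule keeps that patient in the risk set until day 28 after the dose, although nobody was assessing CAE status. That time adds to the denominator and can contribute no event, so the estimated hazard falls. Both Kaplan-Meier curves are then somewhat too high. If study withdrawal is similar in the two arms, the effect on the hazard ratio cancels. If it differs, the arm with more leavers has its hazard diluted more and looks better than it should.

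This also sits oddly with the SAP's general approach. SAP 4.4 uses only observed data for variables other than the categorical OCS endpoints, the primary analysis places early stoppers in the lowest category, and SAP 6.4.9.2 does not credit a missing diary night as awakening-free. Here, unobserved time is scored favourably.

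**Working it through.** **Figures in the documents.** Neither document gives a CAE rate, a withdrawal rate, an event count or a power figure for this endpoint, so there is no figure on this point to reproduce. The only sample-size statement is for the primary endpoint. With average category probabilities of 0.1762, 0.1070, 0.1703, 0.1073 and 0.4393 (placebo figures from SAP 2.3, odds ratio 2.63), the proportional-odds formula gives N = 12(1.960 + 1.282)² / [(ln 2.63)² × (1 − Σp̄³)] = 149.4 in total, or 75 per group. Power at 76 per group is 90.5%. The stated 76 and 90% are reproduced, and only n = 76 per arm is carried forward.

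**Largest gap per patient.** Dosing is by "sc injections in the upper arm(s) once every 4 weeks for a total of 6 doses" (Protocol 5.1), and the window closes 28 days after the last dose. The gap runs from 0 (contact continues through the window) to 28 days (contact ends on the dosing day).

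**Assumptions.** 76 per arm; 1.5 CAEs per year on placebo; true hazard ratio 0.6 or 1; last dose spread evenly over weeks 0-16 (mean week 8); half or all of the stoppers leave the study; mean gap 2 weeks or full gap 4 weeks.

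**Unobserved time per arm, if every stopper leaves event-free.** A stopper contributes on average 8 + 4 = 12 weeks and a completer 24. With stopping proportion p, time at risk is 76 × [(1 − p) × 24 + p × 12] and unobserved time is 76 × p × gap.

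| p | time at risk (weeks) | unobserved, 2-week gap | unobserved, 4-week gap |
|---|---|---|---|
| 5% | 1778 | 7.6 (0.43%) | 15.2 (0.85%) |
| 10% | 1733 | 15.2 (0.88%) | 30.4 (1.75%) |
| 15% | 1687 | 22.8 (1.35%) | 45.6 (2.70%) |
| 30% | 1550 | 45.6 (2.94%) | 91.2 (5.88%) |

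**Hazard ratio.** If a fraction f of an arm's time is unobserved, its hazard is diluted by about (1 − f). The ratio of the hazard ratio under the SAP rule to that under a capped rule is therefore about (1 − f_active)/(1 − f_placebo). This ignores truncation of time at the first event. Simulated Cox fits with exponential event times agree:

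| stopping, active vs placebo | case | by hand | simulated |
|---|---|---|---|
| 10% vs 10% | any | 1.000 | 1.000 |
| 15% vs 5% | half leave, mean gap 2 weeks | 0.99325/0.99785 = 0.995 | 0.995 |
| 15% vs 5% | all leave, 4 weeks | 0.9730/0.9915 = 0.981 | 0.980-0.981 |
| 30% vs 10% | half leave, mean gap 2 weeks | 0.9853/0.9956 = 0.990 | 0.989-0.990 |
| 30% vs 10% | all leave, 4 weeks | 0.9412/0.9825 = 0.958 | 0.956 |

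Reversing the arms gives 1.005 to 1.021 and 1.011 to 1.048. In the most extreme case with true hazard ratio 0.6, the estimate was 0.582 under the SAP rule and 0.608 with the cap.

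**Effect on testing.** Under a true hazard ratio of 1, simulated rejection stayed at 0.04 to 0.06 with either rule. Under 0.6, the largest difference in favour of reslizumab was 0.525 against 0.444, in that same extreme case. With the arms reversed it was 0.407 against 0.475.

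**Kaplan-Meier.** If last contact is 0-7 days after the last dose (mean gap 28 − 3.5 = 24.5 days), the placebo event-free probability at week 24 is overstated by about 0.5 points at 10% study withdrawal and about 1 point at 20%. A gap of some 24 days is an upper-range assumption.

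**The case against.** The strongest reply is that few patients are touched and the effect is small.

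- **Scope.** A reader might infer that every early stopper adds unobserved time. The documents do not support that. Patients with an on-treatment CAE are not censored, and those who stay in the study are asked to keep attending. Only event-free patients who leave before last dose + 4 weeks matter.
- **Contact after leaving.** Protocol 3.16.4 also asks leavers to return for the follow-up visit if possible, and 4.5.2 asks for efforts to trace patients lost to follow-up, so some CAEs could still come to light. This stands in part. CAEs are not in the minimum data list, and the CAE row of Protocol Table 5 stops at visit 19, although Protocol 3.1.4.1 mentions CAEs at the follow-up evaluation.
- **Gap.** Patients are dosed at 4-weekly visits, so one who stops at the next visit has a gap near zero. SAP 4.5 anticipates early termination visits 3 to 5 weeks after the last dose. This stands, and the 24-day gap is not typical.
- **Precision.** With 1-2 CAEs per year on placebo and hazard ratio 0.6, about 46-78 first events are expected, so SE(log HR) is about 2/√78 = 0.23 to 2/√46 = 0.30. A 2% shift is under a tenth of a standard error.
- **Stakes.** The endpoint is outside the fixed sequence (SAP 4.3), and SAP 5.2 already plans plots of time to treatment discontinuation by arm. Those plots can reveal imbalance in stopping drug; they do not correct the time at risk.

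None of this supplies a cap. SAP 4.4 is a general statement and does not displace an explicit censoring date.

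**Conclusion.** The point holds, at low severity. As written, the rule counts up to 4 weeks per patient as exacerbation-free for event-free patients who leave the study before last dose + 4 weeks. The direction is clear: the Kaplan-Meier curves are slightly too high, and the hazard ratio moves towards the arm losing more patients. The size rests entirely on assumed CAE and withdrawal rates: about 0 with equal withdrawal, 0.5-2% at 15% versus 5%, and 1-5% at 30% versus 10%.

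Two stronger readings are not supported. One is that the rule favours reslizumab: the documents give no withdrawal rates, so imbalance is plausible but undocumented, and its direction is unknown. The other is that the CAE rate, a secondary endpoint in the fixed sequence, carries the same bias. SAP 6.3.3.2 uses the same treatment window but does not say whether follow-up duration in the offset runs past the last contact. That needs to be settled; it is not a demonstrated error.

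**What to change.** In SAP 6.4.2.2, censor patients who discontinue treatment early without an on-treatment CAE at the earlier of last dose + 4 weeks and the last contact at which CAE status was assessed. The documents name no field for that date, so the date of the last visit with a CAE assessment can serve as proxy. Where a later contact establishes CAE status for the whole window, the last dose + 4 weeks date stands.

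In SAP 6.3.3.2, limit the follow-up duration in the negative binomial offset in the same way, so that both CAE analyses use the same observed time at risk. Make both changes before unblinding.

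The cost is a sentence in each section, the minimum of two dates in the programming, and slightly less person-time: at 15% stopping, at most 1.4-2.7% of an arm's time at risk for gaps of 2 to 4 weeks. Patients observed through the window are unaffected.

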6.4.3. Pulmonary Function Tests

6.4.3.1. Variable Definition

Pulmonary function tests will be measured using spirometry, according to ATS/ERS 2005 procedural guidelines. Pre-bronchodilator assessments (FVC, FEV₁, FEF_{25%-75%}) are measured at weeks 4, 8, 12, 16, 20, 24, and 32 (follow-up) and post-bronchodilator assessments (FEV₁) are measured at weeks 4, 12, 20, 24, and 32 (follow-up).

The FVC is the volume of air, in liters (L), that can be forcibly blown out after full inspiration. The FEV₁ is the volume of air (L) that can be forcibly exhaled from the lungs in the first second. The FEF_{25%-75%} is the forced expiratory flow (L/second) at 25% to 75% forced vital capacity. The percent (%) predicted FEV₁ is derived as the actual FEV₁ divided by the standard predicted FEV₁ (multiplied by 100). The National Health and Nutrition Examination Survey (NHANES) III reference equations will be used. An additional correction factor will be applied for Asian patients ([Hankinson et al 2010](#)).

6.4.3.2. Analysis

Summary statistics of actual values and change from baseline to each scheduled visit will be provided by treatment group.

Analysis of the change from baseline to each scheduled visit will be performed using a mixed effect model for repeated measures (MMRM) including fixed effects for treatment, visit, treatment by visit interaction, age group (12 to <18 years and ≥18 years), OCS dose at baseline (>10 mg and ≤10 mg), and sex, height and baseline value as covariates, and patient as a random effect. Age and OCS dose at baseline will be based on data recorded in the clinical database. An unstructured covariance matrix will be used for the within patient correlation modeling. If the fit of the unstructured (UN) covariance matrix fails to converge, the following covariance structures will be tried in order until convergence is reached: first order autoregressive (AR[1]) and compound symmetry (CS). Based on the MMRM model, the treatment effect, the difference from placebo, and the associated 95% CI will be presented together with the corresponding p-value.

The following sample SAS[®] code pertains to the MMRM analysis.

```
proc mixed data=<<>>;
  class patient visit treatment strata1 strata2 sex;
  model change=treatment strata1 strata2 sex height baseline visit treatment*visit
    /ddfm=kr alpha=0.05;
```

```
repeated visit /type=un subject=patient r;  
lsmeans treatment*visit / diff cl;  
ods output lsmeans=<<>>;  
ods output diffs=<<>>;  
run;
```

Model results will only be reported if there are at least 15 patients contributing to the analysis in each treatment group; otherwise only the descriptive statistics will be displayed. A line graph presenting the LS mean change from baseline over time (at each visit) will be provided for pre-bronchodilator FEV₁, FVC, FEF_{25%-75%} by treatment group.

Pre-bronchodilator FEV₁ at Week 24 will additionally be examined for the selected subgroups defined in Section 3.4. The analysis of subgroups will use a MMRM model similar to the one described above. Subgroups will be presented graphically using forest plots.

The proportion of patients achieving an increase of ≥ 100 mL in FEV₁ from baseline to each scheduled visit will be summarized. A stratified (based on randomization strata) Cochran-Mantel-Haenszel (CMH) test will be used to analyze the proportion of patients achieving an increase of ≥ 100 mL in FEV₁ from baseline to Week 24.

6.4.4. AQLQ +12

6.4.4.1. Variable Definition

The AQLQ +12 is a modified version of the standardized AQLQ which measures functional impairments experienced by adults ≥ 17 years of age. The AQLQ +12 is valid for patients aged 12-70 years.

The AQLQ +12 is a 32-item instrument administered as a self assessment at weeks 4, 8, 12, 16, 20, and 24. Patients are asked to recall their experiences during the previous 2 weeks and to score each question on a 7-point scale (7 = no impairment, 1 = severe impairment).

The 32 questions (items) in the AQLQ +12 are divided into 4 domains:

- Activity limitations: Items 1-5, 11, 19, 25, 28, 31, 32

- Symptoms: Items 6, 8, 10, 12, 14, 16, 18, 20, 22, 24, 29, 30
- Emotional function: Items 7, 13, 15, 21, 27
- Environmental stimuli: Items 9, 17, 23, 26

